Diabetes mellitus is a severe concern of mankind in the recent years and is a global health situation irrespective of the socioeconomic profile and geographic location of the population. A variety of statistics across the globe has been clearly representing that diabetes mellitus has attained a pandemic form(1). World Health Organization (WHO) has indicated that more than 80% of the diabetes deaths occur in low and middle revenue countries. It has also been expected that diabetes will be the seventh important cause of death in 2030(2). According to International Diabetic Foundation (IDF), throughout 2012, more than 371 million people suffer from diabetes. The number of people with diabetes is rising in every country and about 4.8 million citizens die every year. More than 471 billion USD were used up on healthcare for diabetes (3). The increase in type 2 diabetes is related to lifestyle changes that have resulted in overweight, obesity, and decreased physical activity levels. These environmental changes, superimposed on genetic predisposition, increase insulin resistance, which, in concert with progressive- β -cell failure, results in rising glycemia in the nondiabetic range. In addition to the risk for diabetes, insulin resistance and impaired insulin secretion are accompanied by a host of major cardiovascular disease (CVD) risk factors including hypertension and dyslipidemia. Further reduction in insulin secretion over time results in increasing glycemia and the development of diabetes, which in turn is associated with the development of microvascular and cardiovascular complications.

In the last few years, there has been an exponential increase in the field of herbal medicinal study which is ahead of popularity both in the developing and developed countries for the reason of their natural origin and less side effects (4). Despite extensive progress in the treatment of diabetes by oral hypoglycemic agents, the exploration for newer drugs continues because of the several restrictions found in the usage of synthetic drugs. Medicinal plants supply a potential source of hypoglycemic drugs possessing the dynamic compounds which have been used in the treatment of diabetes and they are highly praised for their therapeutic properties in the traditional medicine system(5).

Diabetes prevention

5. To evaluate the preventive efficacy of polyherbal formulation(test) by assessing the effect on Glucose intolerance.
6. To evaluate effect of polyherbal formulation (test) on the insulin.

7. To evaluate the potential preventive effect of polyherbal formulation for developing a preventive strategy for prevention of DM.

Material and Method:

Chemicals:

Liver function test kit

Renal function test kit

Lipid profile kit

Insulin kit

Glucose Reagent Kit

Glucose (pharmaceutical grade)

Polyherbal formulation:

In the last few years, there has been an exponential increase in the field of herbal medicinal study which is ahead of popularity both in the developing and developed countries for the reason of their natural origin and less side effects (4).

Despite extensive progress in the treatment of diabetes by oral hypoglycemic agents, the exploration for newer drugs continues because of the several restrictions found in the usage of synthetic drugs. Medicinal plants supply a potential source of hypoglycemic drugs possessing the dynamic compounds which have been used in the treatment of diabetes and they are highly praised for their therapeutic properties in the traditional medicine system.(5) Polyherbal formulation of Eastern Medicine used in this research is popularly utilized in traditional medicine in various countries to control and treat diabetes. These herbs are used extensively. Four important herbs among these are selected for the preventive effect of these products. These includes Colosynth seed, Occimum tenuiflorum seed, Holarrhena antidysenterica seeds, Gymnemia Sylvester leaves. These herbs have proved to produce anti-diabetic effect by modulating beta-cell in pancreatic islet cell, enhanced insulin secretion, hypoglycemic, anti-hyperlipidemic, anti-Cholesterolic effects on CVS and diabetes. (18-21)

Study Design:

Three arm parallel Observational Cross-Sectional and Case-Crossover clinical trial (Phase 1)

Groups:

Groups and Interventions

| Groups/Cohorts | Interventions |
|--|--|
| Group A Pre-diabetic placebo Group of pre-diabetics receiving placebo BD for six weeks | |
| Group B Pre-diabetic test Group of Pre-diabetic receiving polyherbal / test candidate 900mg in two divided doses for six weeks | Dietary Supplement: Polyherbal formulation Test candidate will be administered per oral before / with meal in two divided doses |
| Group C Diabetic test Early onset of Diabetes mellitus receiving polyherbal formulation 1800mg in two divided doses for six weeks | Dietary Supplement: Polyherbal formulation Test candidate will be administered per oral before / with meal in two divided doses |

Study Description:

Brief description:

Primary protocol to this study is to develop a natural remedy to prevent diabetes mellitus in pre-diabetic state and elaborate the effectiveness of polyherbal formulation for carrying out Phase-II, III and IV. It also aimed at to see the level of difference of glucose tolerance and impaired fasting glucose and impaired glucose tolerance between pre-diabetic and diabetic to evaluate the potential benefit for treatment of insulin resistance and sensitivity. To see the for prevention of Diabetes Mellitus (DM) and stopping / delaying the onset of DM.

Detailed description:

This study is a clinical trial study to evaluate the potential of prevention in pre-diabetics and to prevent onset of diabetes mellitus. For this purpose, volunteers will be enrolled in the study by observing the Helsinki Declaration for clinical trials.

volunteers will be screened for the impaired glucose tolerance or impaired fasting glucose or at risk to develop diabetes mellitus type 2.

On screening, pre-diabetics and early onset diabetics with no previous history of treatment etc will be grouped into A and B.

Biochemical evaluations will be carried out at base line and followed by three weeks intervention and evaluation of biomarkers and at sixth week for further evaluation.

Collected data will be evaluated for primary out comes and secondary out come. statistical analysis will be done.

Method:

Step 1: Consent, observation of Ethical Principles of Declaration of Helsinki, questionnaire and screening of targeted population for impaired fasting glucose (IFG) and impaired glucose tolerance(IGT), (16-17)

State FPG Level 2-h plasma glucose

In OGTT (mg/dl)

Impaired Fasting Glucose = 100-125 <200

Isolated IFG = 100-125 <140

Impaired Glucose Tolerance = <126 140-199

Isolated IGT = <100 140-199

Step 2: Individuals with IFG & IGT evaluated for age, family history of diabetes in first degree relation, BMI = 35 kg/m³ will be evaluated for following profiles on two week basis with baseline

1. Lipid profile for elevated triglycerides, low HDL, Cholesterol
2. Hepatic functions: SGPT, SGOT, ALT,
3. Renal Function test for Creatinine, Urea
4. Insulin level

Step 3: At high risk population with impaired FG & IGT and underlying or corresponding diseases ,(8-11) population will be given oral polyherbal formulation of Eastern Medicine for six weeks.

Step 4: data collected and interpreted with statistical significance

Eligibility Criteria:

| | |
|-----------------------------|---|
| Study Population: | 
• community samples will be obtained from the area of Bahawalpur• Model Town A, B, and• remote areas of district Bahawalpur consisting of Khairpur Tamewali city population |
| Sampling Method: | Probability Sample |
| Minimum Age: | 18 Years |
| Maximum Age: | 59 Years |
| Sex: | All |
| Gender Based: | No |
| Accepts Healthy Volunteers: | Yes |
| Criteria: | Inclusion Criteria: 
• Age: 18-59• Impaired Fasting Glucose (100-125mg/dl) |

- Impaired Glucose Tolerance (140-199mg/dl) 2h-75gm OGTT
- History of Diabetes in first degree relation with one condition
- At high risk with BMI > 35%
- Early onset diabetic / accidental on screening (glucose >200mg/dl)

Exclusion Criteria:

- on renal dialysis;
- an acute or terminal illness or serious mental illness;
- history of recent coronary event within the last 12 months;
- a recent history of acute medical problem or admission to hospital;
- any other severe medical conditions that need intervention / treatment
- has poor short-term prognosis (expected death in <2 years);
- is planning to travel for longer than 6 weeks during the 6-week intervention period; or
- is with compromised liver / kidney / cardiac function
- older patients of DM taking any form of medication / intervention

Out Comes:

Study outcomes will be measured by various biomarkers and beneficial effects / toxic effect will be assessed by certain blood biomarkers as followed.

Primary outcomes:

1. Enhancement of Glucose Tolerance
2. Enhancement of Impaired Fasting Glucose Tolerance
3. HbA1c level of reduction

Secondary Outcomes:

1. Lipid Profile including
 - a. Level of Cholesterol
 - b. Triglycerrhides
 - c. Low density lipid (LDL)
 - d. High density lipid (HDL)

Unspecified Outcomes:

1. Liver Function
 - a. Serum Glutamate Oxaloacetate Transaminase (SGOT) level
 - b. Serum Glutamate Pyruvate Transaminase (SGPT) level
 - c. Alkaline Phosphatase level

2. Kidney Function
 - a. Serum Creatinine level
 - b. Blood Urea Nitrogen level

Noting of Adverse events:

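### The design label and the grouping sentence contradict the three-group table, and no rule in the text shown decides which pre-diabetics receive placebo

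*Protocol*

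**What the plan says.** The Study Design section of the protocol labels the study a "Three arm parallel Observational Cross-Sectional and Case-Crossover clinical trial (Phase 1". The Groups and Interventions table below it has three rows:

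- The first row is the placebo group: "Group A Pre-diabetic placebo Group of pre-diabetics receiving placebo BD for six weeks".
- The second row keeps the same disease state but moves to the product: "Group B Pre-diabetic test Group of Pre-diabetic receiving polyherbal / test candidate 900mg in two divided doses for six weeks".
- The third row is the only one for people with diabetes, again on the product: "Group C Diabetic test Early onset of Diabetes mellitus receiving polyherbal formulation 1800mg in two divided doses for six weeks".

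The Detailed description, under Study Description, says: "On screening, pre-diabetics and early onset diabetics with no previous history of treatment etc will be grouped into A and B".

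Step 3 of the Method names the "At high risk population with impaired FG & IGT and underlying or corresponding diseases" and states that this "population will be given oral polyherbal formulation of Eastern Medicine for six weeks".

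Under Eligibility Criteria, the sampling method is given as "Probability Sample". The text shown has no other statement on how people are selected for, or assigned to, a group.

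**The concern.** The design line joins terms that describe different kinds of study. A parallel trial compares groups that are given different treatments. An observational study assigns no treatment. A case-crossover study compares each person's exposure before an event with the same person's exposure in a control period. A cross-sectional study looks at one time point. Someone conducting or analysing the study cannot tell from this line which comparison is intended.

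The grouping sentence adds a practical difficulty. Staff who followed it literally would put people with diabetes into groups that the table reserves for pre-diabetics, and nobody would enter Group C.

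The most serious gap is the route into A or B. Both groups are defined by the same disease state, so eligibility cannot separate them, and something else must decide who gets placebo. If that is left to circumstance, the two groups may differ before treatment starts. Allocation cannot be repaired once volunteers are enrolled.

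**Working it through.** No arithmetic applies, because the protocol states no sample size, variance, ratio or assignment rule. The check sets the passages side by side.

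**1. Label against table.**

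- *Three arm parallel*: agrees with the table, which has three concurrent groups with one regimen each.
- *Observational*: does not agree. The protocol itself assigns placebo or product for six weeks, and the Detailed description calls the study a clinical trial.
- *Case-crossover*: does not agree. Nobody changes treatment, and no event or control period is defined.
- *Cross-sectional*: fits screening and baseline at most (objectives 1 and 2), because biomarkers are measured again during treatment.

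**2. Grouping sentence and Step 3 against table.**

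| Place | Who | Where they go | Placebo mentioned |
|---|---|---|---|
| Group table | Pre-diabetics | A or B | Yes, A |
| Group table | Early-onset diabetics | C | No (product) |
| Detailed description | Both populations | A and B only | No |
| Method, Step 3 | High-risk people with impaired glucose and other disease | No group named | No |

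The Detailed description contradicts the table directly: two populations enter two groups, both of which the table defines as pre-diabetic. Step 3 is different. It assigns nobody to a group, and its disagreement with the table is one of omission: it mentions the product and is silent on placebo, although Group A is drawn from pre-diabetics.

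**3. Search for an A or B rule.** The body of the protocol shown contains no randomisation, ratio, concealment, alternation or other rule. Randomisation appears only in titles in the reference list. The sampling method under Eligibility Criteria concerns how people are drawn from the community, not which treatment they then receive.

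**4. What depends on the rule.** By the group definitions:

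- B versus A: same disease state, product against placebo.
- C versus A: disease state differs as well as treatment.
- C versus B: disease state differs, and so does the stated amount (1800mg against 900mg).

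A placebo-controlled answer to objective 5, preventive efficacy, can therefore come only from B versus A. That A and B differ in treatment alone holds for the group labels. Whether it holds for the people in the groups depends on the missing rule.

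**5. Size.** If a baseline factor X is linearly related to an outcome with slope b, the B-minus-A difference carries an extra term

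b × (mean of X in B − mean of X in A).

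Candidates for X in the protocol are baseline glucose, BMI, family history, other disease and recruitment area (Model Town or Khairpur Tamewali). The protocol supplies neither the slope nor the imbalance for any of them, so neither the size nor the direction can be calculated.

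**The case against.** The strongest reply is that most of this is wording. A reader with the table in hand would take the grouping sentence as a slip for A, B and C and would ignore the misfitting labels. The protocol never claims randomisation and never names B versus A as its test. An early-phase study may assign treatment non-randomly, and stating whatever rule is used would cure the defect.

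Much of that stands. The label and the grouping sentence are indeed corrections of wording, and a declared non-random rule would be coherent, which is why the fix allows one. The reply does not supply the rule, however. Even with the sentence read as A, B and C, nothing shown divides pre-diabetics between placebo and product. Nor can this wait for a statistical analysis plan, because allocation must be settled before the first volunteer is treated. One part of the protocol was not available here, so a rule could stand there; it would still not remove the conflict between the passages quoted.

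A reader might infer three stronger points that the documents do not support:

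- *Step 3 abolishes the placebo group, or allocates by risk.* Step 3 names a narrower population, and it neither forms groups nor says that nobody receives placebo.
- *The stated aim of comparing pre-diabetics with diabetics means C versus B, and so is confounded by dose.* The Brief description names no groups and does not restrict the comparison to treated people. A baseline comparison of A and B together with C fits it equally well.
- *B versus A is biased.* No imbalance is shown; it is only left unprevented.

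**Conclusion.** The point holds and should be settled before enrolment. Two statements are wrong as written: the observational and case-crossover labels do not fit protocol-assigned treatment, and the grouping sentence contradicts the group table. Step 3 needs wording that agrees with the table, but is not a contradiction of the same weight. The missing A or B rule is what makes this more than editing, because it leaves unprotected the only placebo comparison defined within one disease state.

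The consequence is possible confounding of unknown size and direction. The conclusion assumes that the group table expresses the intended design and that no assignment rule stands in the part of the protocol not shown.

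**What to change.** 1. In Study Design, keep the three-arm parallel description. Remove the observational and case-crossover terms from the treatment phase, and limit cross-sectional to screening and baseline.
2. Reconcile the grouping sentence in the Detailed description, and the wording of Step 3, with the Groups and Interventions table.
3. Allocate pre-diabetics to A or B at random from a concealed list, state the ratio, and describe Group C as a separate non-randomised cohort.
4. If assignment is meant to be non-random, state the rule instead, and do not present B versus A as a randomised or causal placebo comparison.

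Items 1, 2 and 4 cost protocol wording only. Item 3 also needs someone not involved in enrolment to prepare and hold the list, which is a small added task.

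### The sentence placing screened volunteers sends early onset diabetics to Groups A and B, the group table sends them to C, and the glucose limits separating the groups do not agree

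*Protocol*

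**What the plan says.** **Placement.** The Detailed description (Protocol, Study Description) states: "On screening, pre-diabetics and early onset diabetics with no previous history of treatment etc will be grouped into A and B". Group C is not mentioned there.

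**Group table.** The table under Groups defines three groups. The placebo arm is given as "Group A Pre-diabetic placebo Group of pre-diabetics receiving placebo BD for six weeks". The treated arm drawn from the same population is given as "Group B Pre-diabetic test Group of Pre-diabetic receiving polyherbal / test candidate 900mg in two divided doses for six weeks". The third arm takes the diabetics: "Group C Diabetic test Early onset of Diabetes mellitus receiving polyherbal formulation", with a stated amount of 1800 mg. The Study Design line calls the trial three-arm.

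**Screening limits.** Step 1 of the Method tabulates fasting plasma glucose (FPG) and 2-hour OGTT glucose together. Its first row reads "Impaired Fasting Glucose = 100-125 <200", that is, FPG 100 to 125 with a 2-hour value below 200 mg/dl. Its row for impaired glucose tolerance (IGT) requires FPG below 126 with a 2-hour value of 140 to 199.

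**Inclusion bullets.** The Eligibility Criteria give impaired fasting glucose (IFG) as 100 to 125 with no 2-hour limit, and IGT as a 2-hour value of 140 to 199 with no FPG limit. Early onset diabetics, or those found by chance at screening, enter with a glucose above 200 mg/dl. The bullet does not say whether that value is fasting, 2-hour or random.

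**The concern.** Group A is the only placebo group, and B is the only treated group meant to come from the same population. A versus B is therefore the one comparison with placebo that is not tied to disease state. The primary outcomes are glucose tolerance, fasting glucose and HbA1c, so glycaemic state at entry both decides placement and bears directly on what is measured. If diabetics enter A and B, those groups are no longer the pre-diabetic population that the table names. If diabetics make up B alone, treatment and disease state cannot be separated.

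Placement also decides what a person receives as the table stands: placebo, the Group B amount or the Group C amount. Limits that let one screening result be placed in different ways leave that decision to whichever section the screening staff happen to use.

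**Working it through.** No sample size, power or error rate enters this point, so the check is a comparison of texts followed by a logical test of the limits.

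**1. Sentence against table.** The sentence can be read in two ways.

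- Both kinds of volunteer go into both groups. A and B then contain diabetics, whereas the table makes both pre-diabetic.
- Pre-diabetics go to A and diabetics to B, respectively. B is then diabetic, whereas the table makes B pre-diabetic and places diabetics in C.

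Both readings conflict with the table, and neither sends anyone to C.

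**2. Limits applied to example results.** The inputs are the Step 1 table, the inclusion bullets, and the diabetic line (above 200) read first as a fasting value and then as a 2-hour value. A random-sample reading cannot be tested from these pairs. Values are FPG / 2-hour in mg/dl.

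| Result | Step 1 | Inclusion bullets | Above 200, fasting | Above 200, 2-hour |
|---|---|---|---|---|
| 110 / 130 | IFG | IFG | no | no |
| 95 / 150 | IGT | IGT | no | no |
| 205 / 210 | neither | neither | yes | yes |
| 115 / 215 | neither (215 is not below 200) | IFG | no | yes |
| 115 / 200 | neither (200 is not below 200 and is outside 140–199) | IFG | no | no |
| 130 / 150 | neither (130 is not below 126) | IGT | no | no |
| 90 / 200 | neither | neither | no | no |

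The first three rows show that many results are placed the same way whichever text is used. The next three show where the texts part.

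**3. Consequence for 115 / 215**, taking the table's populations for A/B and C:

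- bullets, above 200 read as fasting: A/B only;
- bullets, above 200 read as 2-hour: both A/B and C, with no precedence rule;
- Step 1, above 200 read as 2-hour: C only;
- Step 1, above 200 read as fasting: no group.

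**4. Boundary.** A 2-hour value of exactly 200 lies above the IGT range, which ends at 199, and is not above 200. So 90 / 200 meets no glucose line in either text.

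**The case against.** The best defence is that the placement sentence is a slip. The design line says three arms, the group names carry the disease state, and adding Group C to the sentence would make the document consistent. Staff would have to ignore the groups' own labels to put a diabetic into A or B. This is persuasive about what was probably meant. It does not remove the need for correction, because no other sentence says how people move from screening into groups.

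Second, Step 1 can be seen as the operative definition and the inclusion bullets as shorthand for states already defined there. On that reading 115 / 215 is simply not IFG, and the overlap disappears. This is fair. It means that the IFG and IGT differences are an inconsistency of wording and the missing sample type an ambiguity; only the placement sentence is a contradiction. The double classification of 115 / 215 needs two conditions together: the IFG bullet read alone, and the diabetic value read as 2-hour. The gap at exactly 200 is minor, and meeting no line is not a fault in itself, since not eligible is a legitimate outcome.

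Third, a reader might infer that eligibility of the isolated states is unresolved, because Steps 2 and 3 join IFG and IGT with an ampersand. The document does not support that. "Isolated IFG = 100-125 <140" lies inside the Step 1 IFG row and "Isolated IGT = <100 140-199" lies inside the IGT row (FPG below 126), so both isolated states qualify. The ampersand can simply name two categories, in line with the alternatives in the screening sentence: "volunteers will be screened for the impaired glucose tolerance or impaired fasting glucose or at risk to develop diabetes mellitus type 2". The family-history bullet also carries a combination condition of its own, though a vague one.

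**Conclusion.** The placement sentence is wrong as written against the group table, and it should be fixed. The differing limits and the unspecified sample type are lesser faults that bear on the same decision.

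A reader might go further and conclude that B versus A is biased, or that diabetics will in fact enter A and B. The Protocol does not show this. The table and design line point the other way, and no screening distribution is given from which to count the people affected. The glucose pairs above are examples, not frequencies. The conclusion rests on reading the Step 1 columns as FPG then 2-hour glucose, as their header labels them.

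Whether risk factors alone, or healthy-volunteer status without impaired glucose, are enough for entry is a separate and minor clarification.

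**What to change.** 1. Reconcile the grouping sentence in the Detailed description with the group table, so that both assign the same populations to A, B and C.
2. Use one set of joint fasting and 2-hour limits in both the Step 1 table and the inclusion bullets.
3. State the sample type for the Group C glucose value.
4. Make the ranges non-overlapping and without gaps, including a 2-hour value of exactly 200, so that each screening result leads to exactly one of A/B, C or not eligible.

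The sponsor chooses the limits; this review proposes none.

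The cost is mainly protocol wording, since Step 1 already screens on both measurements. The Protocol does not say whether people found diabetic by chance at screening have both values, so joint limits may mean both tests for them. Some volunteers may be reclassified or not enrolled; how many depends on the limits chosen and cannot be known from the document.

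### The Step 2 liver panel names one aminotransferase twice and leaves out alkaline phosphatase, which the outcome list requires

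*Protocol*

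**What the plan says.** Method, Step 2 lists four groups of tests for people with impaired fasting glucose and impaired glucose tolerance, who "will be evaluated for following profiles on two week basis with baseline". The liver line is "Hepatic functions: SGPT, SGOT, ALT" and the kidney line is "Renal Function test for Creatinine, Urea".

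The outcome section, under Unspecified Outcomes, lists three liver markers: "Serum Glutamate Oxaloacetate Transaminase (SGOT) level", "Serum Glutamate Pyruvate Transaminase (SGPT) level" and "Alkaline Phosphatase level". Its kidney markers are serum creatinine and "Blood Urea Nitrogen level".

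Two other places bear on the liver tests, and neither names an analyte. The materials list includes a liver function test kit with contents unstated. The Detailed description says "Biochemical evaluations will be carried out at base line and followed by three weeks intervention and evaluation of biomarkers and at sixth week".

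**The concern.** The panel to be drawn and the outcomes to be reported should contain the same liver markers, and they do not. The Step 2 line repeats one enzyme under a second name, and the third listed outcome is absent.

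This bears on safety. Objective 4 assesses the safety profile, and whether the formulation is acceptable to take further, from its effect on blood markers. The opening of the outcome section likewise says that toxic effects will be judged from the biomarkers it lists. Without alkaline phosphatase the liver assessment rests on two aminotransferases, and a cholestatic pattern of injury would be harder to see.

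The omission also cannot be repaired at the analysis stage. An analysis plan can decide how to summarise a marker, but it cannot supply one that was never assayed.

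**Working it through.** The plan states no figure to reproduce, so the check is an item-by-item comparison of the two lists. The one fact taken from outside the protocol is standard nomenclature: SGPT (glutamate-pyruvate transaminase) and ALT (alanine aminotransferase) are the same enzyme.

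| Liver marker | Step 2 panel | Outcome list |
|---|---|---|
| SGOT | yes | yes |
| SGPT (= ALT) | yes, entered twice | yes |
| Alkaline phosphatase | no | yes |

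- Entries in the Step 2 liver line: 3. Distinct analytes: 3 − 1 duplicate = 2.
- Distinct analytes in the liver outcome list: 3.
- Listed liver outcomes covered by Step 2: 2 of 3. Not covered: 1 of 3, alkaline phosphatase.

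**Does any other procedure text supply the missing marker?** The kit entry and the baseline, week 3 and week 6 sentence name no analytes, so they neither include nor exclude it. Step 2 is the only procedure text that itemises liver tests.

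**Is Step 2 a complete list of the study's tests?** No. It omits HbA1c, a primary outcome, and LDL, a secondary outcome. It is also addressed to people with impaired fasting glucose and impaired glucose tolerance and does not mention the diabetic Group C. Absence from Step 2 therefore does not prove that a marker will go unmeasured.

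**Kidney line.** Creatinine agrees in both places. The second marker is urea in Step 2 and blood urea nitrogen in the outcome list, and no unit is given for either. If both were reported in mg/dl (an assumption), the ratio would be the molar mass of urea over that of its two nitrogen atoms: 60.06 / 28.01 = 2.14. In mmol/l a mass-based factor of this kind would not apply.

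**The case against.** The strongest reply is that the protocol does state an intention to measure alkaline phosphatase, because the outcome section names it among the biomarkers by which outcomes will be measured. Since Step 2 also lacks HbA1c and LDL, the natural reading is that Step 2 is incomplete, not that it overrides the outcome list. This stands. A reader might infer from Step 2 that alkaline phosphatase will be tested at no time point, baseline included. The protocol does not support that: a site reading the whole document could still collect it.

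A second reply is that ALT is simply a slip for ALP, which the outcome list already resolves. That is plausible, since each list has three liver entries and two of them match. But the protocol does not say so, and the line ends on a comma, so the list may be unfinished. A probable slip in the text from which samples are ordered still needs correcting.

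A third reply is that these markers are neither primary nor secondary outcomes and that no decision rule uses alkaline phosphatase. That is true and limits the weight of the point, although Objective 4 still relies on blood markers for safety.

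On the kidney line, a reader might infer that urea recorded as blood urea nitrogen would roughly double the values and imitate a kidney signal. The protocol does not support this either. The 2.14 factor needs mg/dl for both, which is not stated, and nothing says that one would be recorded under the other's name. If one analyte is used throughout, a constant factor cancels in percent change from baseline and in ratios between arms.

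**Conclusion.** The two liver lists disagree, and the error lies in operational text. Step 2 covers 2 of the 3 listed liver markers, enters one of them twice and omits alkaline phosphatase. The consequence is conditional: a site working from Step 2 alone would not collect that marker, and its missed baseline could not be recovered later, whereas a site that also follows the outcome section might collect it.

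The conclusion rests on SGPT and ALT being one enzyme and on Step 2 being the only procedure text that itemises liver analytes. It does not depend on ALT being a typing error. The effect is confined to the completeness of the liver safety data; the primary and secondary efficacy outcomes are not affected. The difference between urea and blood urea nitrogen is a naming mismatch only and adds nothing to the weight of the point.

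**What to change.** Before enrolment, replace ALT with alkaline phosphatase in the Step 2 liver line, so that it reads SGOT, SGPT and alkaline phosphatase and matches the outcome section whenever the liver panel is drawn. This leaves the timing of sampling as it is.

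As a minor tidy-up, choose either urea or blood urea nitrogen and use that name, with its unit, in both Step 2 and the outcome section.

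The cost is a short text correction and a small amount of reagent. The test can be run on the same serum sample, with the chemistry analyser already listed under Machines.
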